# 4.1.6 Packaging, labelling, and re-supply

Trial medication will be labelled with the trial identification and medication code number. It will be dispensed as indicated in the Flow Chart. At each dispensing, an appropriate number of tablets (empagliflozin and/or placebo-to-match empagliflozin) plus some reserve will be given to the patient.

Supply and re-supply will be managed by the IRT.

For details of packaging and the description of the label, refer to the ISF.

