# 5.1.2 Secondary endpoints

The key secondary endpoints to assess efficacy are as shown below. Throughout this CTP, the term "baseline" refers to the 4 week period prior to randomisation for the rate of symptomatic hypoglycaemic AEs with confirmed plasma glucose < 54 mg/dL (< 3.0 mmol/L) and/or severe hypoglycaemic AEs and the 2 week placebo run-in period for the mean daily insulin requirement and CGM.

- Incidence rate of symptomatic hypoglycaemic AEs with confirmed plasma glucose < 54 mg/dL (< 3.0 mmol/L) and/or severe hypoglycaemic AEs per patient-year from Week 5 to Week 26

  - o severe hypoglycaemia is defined as an event requiring the assistance of another person to actively administer carbohydrate, glucagon or other corrective actions. Plasma glucose concentrations may not be available during an event, but neurological recovery following the return of plasma glucose to normal is considered sufficient evidence that the event was induced by a low plasma glucose concentration (see Section 5.3.5.2)
  - The rate will be calculated from Day 29 (start of week 5) up to Week 26 cut-off date (to be defined in the Trial Statistical Analysis Plan, TSAP)
- Incidence rate of symptomatic hypoglycaemic AEs with confirmed plasma glucose < 54 mg/dL (< 3.0 mmol/L) and/or severe hypoglycaemic AEs (see Section 5.3.5.2) per patient-year from Week 1 to Week 26
  - o the rate will be calculated from the date of first study medication intake up to Week 26 cut-off date (to be defined in the TSAP)
- Change from baseline in body weight (kg) after 26 weeks
- Change from baseline in the percentage of time spent in target glucose range of > 70 to ≤ 180 mg/dL (> 3.9 to ≤ 10.0 mmol/L) as determined by continuous glucose monitoring (CGM) in Weeks 23 to 26
- Change from baseline in the inter quartile range (IQR) as determined by CGM in Weeks 23 to 26
- Change from baseline in total daily insulin dose (TDID), U/kg, after 26 weeks
- Change from baseline in systolic blood pressure (SBP) after 26 weeks
- Change from baseline in diastolic blood pressure (DBP) after 26 weeks

c03024901-03 Trial Protocol Version 3.0

Page 46 of 144

04 Jan 2017

Page 47 of 144

Proprietary confidential information © 2017 Boehringer Ingelheim International GmbH or one or more of its affiliated companies

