The analysis of the incidence rate of symptomatic hypoglycaemic AEs with confirmed plasma glucose < 54 mg/dL (< 3.0 mmol/L) and/or severe hypoglycaemic AEs per patient-year from Week 5 to Week 26 will utilise a negative binomial model, with terms for treatment, baseline rate, baseline HbA1c, baseline eGFR and pre-existing insulin therapy as fixed effects, and log (days of follow-up) as an offset. This analysis will include patients from the FAS, including all available on-treatment events from the start of Week 5 (Day 29) up to Week 26 cut-off date. The baseline rate of symptomatic hypoglycaemic AEs with confirmed plasma glucose < 54 mg/dL (< 3.0 mmol/L) and/or severe hypoglycaemic AEs will be calculated based on the event rate during the 4 weeks prior to randomisation.

The analysis of the incidence rate of symptomatic hypoglycaemic AEs with confirmed plasma glucose < 54 mg/dL (< 3.0 mmol/L) and/or severe hypoglycaemic AEs per patient-year from Week 1 to Week 26 will follow the same strategy as the analysis from Week 5 to

Week 26. This analysis will include all patients from the FAS, including all available ontreatment events from date of first study medication intake up to Week 26 cut-off date.

The analysis of change from baseline in SBP after 26 weeks will follow the strategy for the primary endpoint MMRM, with the addition of terms for baseline SBP and baseline SBP by week interaction into the model. This analysis will be performed on the FAS, including all available on-treatment data.

The analysis of change from baseline in DBP after 26 weeks will follow the strategy for the primary endpoint MMRM, with the addition of terms for baseline DBP and baseline DBP by week interaction into the model. This analysis will be performed on the FAS, including all available on-treatment data.

c03024901-03 Trial Protocol Version 3.0

Page 84 of 144

04 Jan 2017

Proprietary confidential information © 2017 Boehringer Ingelheim International GmbH or one or more of its affiliated companies

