6 GENERAL ANALYSIS DEFINITION

6.1 TREATMENTS

There will be six treatment phases in this trial: screening, T1DM therapy optimisation, placebo run-in, study treatment phase (with either empagliflozin or matching placebo), post-treatment and post-study, as follows.

- The screening period starts from the date of informed consent and ends on the day before the start date of the T1DM therapy optimisation period.
- The T1DM therapy optimisation period begins with the start date of the insulin therapy optimisation visit (Visit 2) up to the day before the date of first administration of placebo run-in medication (inclusive).
- The placebo run-in period begins from the date of first administration of placebo run-in medication up to the day before the date of first administration of randomised study medication (inclusive).
- The on-treatment period begins from the date of first administration of study medication up to last intake of study drug + X days (inclusive) [see definition of X in [table 6.7: 1](#)].
- The post-treatment period begins from the last intake of study drug + X days + 1 day up to the last contact date (inclusive). The last contact date is defined as the maximum of (trial completion date, and [last study drug intake + X days + 1 day]).
- The post-study period begins from the last contact date +1 day and ends at trial database lock date.

For efficacy and safety analyses, measurements will still be considered on-treatment during a follow-up period (X days) specific to each parameter. These follow-up periods are defined in [table 6.7: 1](#).

A cut-off date will be used for the analyses at week 26, and will be defined as follows:

- For patients who are still on-treatment at the week 26 visit date:
 - The actual week 26 visit date, if the week 26 visit is within the time window defined in [table 6.7: 2](#).
 - The planned study day 182, if there is no week 26 visit date or if the actual week 26 visit falls outside of the time window for the week 26 visit.
- For patients who prematurely discontinued the treatment prior to week 26:
 - The minimum between (drug stop date + X days) and the actual week 26 visit date, if the week 26 visit is within the time window.
 - The minimum between (drug stop date + X days) and day 182, if there is no week 26 visit date or if the actual week 26 visit falls outside of the time window for the week 26 visit.

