6.6.1.2 Observed cases (OC) analysis

For all efficacy endpoints, it is planned to analyse only the available data that were observed while patients were on-treatment, i.e., excluding the missing data and any values collected after treatment discontinuation. In other words, OC-analysis will be performed and missing data in the analysis will not be replaced.

The OC-technique represents the primary data selection tool that will be used for the primary efficacy analysis in this trial. Subsequent handling of missing data will be performed via a likelihood-based method, and in the case of the primary analysis, will use the mixed-effect model repeated measures (MMRM).

For blood pressure endpoints (SBP and DBP), the OC-technique will be adapted to set values measured after a change in antihypertensive therapy to missing. This technique will be called Observed Cases without values following a change in antihypertensive therapy (OC-H). The following 3 situations are considered to be the start of a change in anti-hypertensive therapy:

- Initiation of additional antihypertensive medication
- Change in dose of antihypertensive medication
- Discontinuation of antihypertensive medication

Antihypertensive medications will be identified based on WHO DD special search categories as specified in [section 9.2](#).

For CGM endpoints, the OC-technique will be adapted to exclude data measured from the date of first intake of paracetamol until the date of last intake of paracetamol + 1 day (inclusive) from the derivation of the endpoints. This technique will be called Observed Cases without values following intake of paracetamol (OC-P). Missing values for entire CGM periods will not be replaced.

Concomitant therapies containing paracetamol will be identified using a WHO DD BI customized query (BICQ) based on Preferred Name (PN) "Paracetamol". This includes all monotherapy and fixed dose combinations (FDC).

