6.6.3 Missing dates and times

Missing or incomplete AE dates are imputed according to BI standards (see “Handling of missing and incomplete AE dates”) (6).

If the date of first drug administration is missing but the patient was randomised, the date of the first drug administration will be set to the date of randomisation. If the date of first administration is partially missing with the month and year present, the day will be set to the date of randomisation if randomisation was in the same month. If randomisation was in the month prior to the first drug administration the missing day will be imputed as the first day of the month.

A missing time of first drug administration will be imputed as 08:00 o'clock in the morning, missing administration times at on-treatment visits will be imputed by 08:00 o'clock in the morning.

As a general rule a missing drug stop date will be imputed according to the following principles:

- If an End of Treatment (EoT) visit or visit 16 is documented, it should be the date of the EoT visit.
- If the date is incomplete with only month and year and the EoT visit is missing, it should be the first day of the following month.
- If the patient is lost to follow-up it should be the date of the last visit + the longest treatment duration based on drug supply + 1 day.
- If a patient died during the course of the trial and no additional information about drug stop date are available, the date of death will be used as drug stop date assuming that the patient took the medication until the day of death.
- All other cases need to be assessed by the trial team on an individual basis, trying to use the points above as guidance.

If only the year of birth is known, the day and month of birth will be imputed as 01 January.

For partial start and stop dates for concomitant therapies (CT) the following derivations will be used to impute 'worst case' values:

- If the day of the end date is missing then the end date is set to last day of the month.
- If the day and month of the end date are missing then end date is set to 31st December of the year.
- If the day of the start date is missing the start date is set to first day of the month.
- If the day and month of the start date are missing then the start date is set to 1st January of the year.

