6.7 BASELINE, TIME WINDOW, AND CALCULATED VISITS

With regard to efficacy and safety endpoints, the term "baseline" refers to the last observed measurement prior to administration of any randomised study medication. For specific endpoints, baseline definitions are as follows:

Hypoglycaemia rate

The event rate of hypoglycaemia (using the respective endpoint definition) during the 4 weeks prior to randomisation (from Day -28 up to Day -1). Collapsing will be performed as per the rules in [sections 5.4.6.3](#) and [5.4.7](#). Rates will be presented per 30 days and also per patient year.

Insulin dose (total daily, total daily basal or total daily bolus)

Mean daily insulin requirement during the run-in period (Visit 5 to Visit 6, excluding day of randomisation). If < 4 days of valid insulin data is reported during the run-in period then the measurement will be considered missing. For data handling rules see [section 5.4.6.2](#).

Table 6.7: 1 Endpoint specific follow-up period for the assignment to active treatment

Endpoint	Last day of assignment to treatment phase (days after study drug stop date)
Efficacy	
HbA _{1c}	7
Body weight	1
Blood pressure	1
Insulin dose	0
Hypoglycaemia	1
Safety	
Adverse events	7
Hypoglycaemia ^[1]	1

*Refer to [section 5.4.4](#) for the assignment of CGM measurements to the on-treatment period

[1] Refers to all hypoglycaemia analyses except the general hypoglycaemia AE analysis by SOC and PT.

Measurements taken after the last intake of study drug and after the end of the endpoint specific follow-up period will be considered off-treatment values.

Efficacy, safety, will be assigned to visits based on time windows around the planned visit dates. These time windows are defined based on the planned number of days after the date of first administration of study drug (see [table 6.7: 2](#)).

Table 6.7: 2 Time windows for HbA_{1c} measurements at scheduled visits after randomisation

Visit number	Visit label	Planned days	Time window (actual days on treatment)	
			Start	End ^A
6	Baseline	0	NA	1 ^B
8	Week 4	28	2	56
9	Week 12	84	57	105
10	Week 18	126	106	154
12	Week 26	182	155	241
14	Week 43	301	242	332
16	Week 52/EOT	364	333	Study drug stop date + X days

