7.5 SECONDARY ENDPOINTS

7.5.1 Key secondary endpoints

- 7.5.1.1 Rate of symptomatic hypoglycaemic AEs with confirmed plasma glucose <54 mg/dL and/or severe hypoglycaemic events confirmed by adjudication

Confirmatory analysis

The analysis of the rate of symptomatic hypoglycaemic AEs with confirmed plasma glucose <54 mg/dL and/or severe hypoglycaemic events confirmed by adjudication will utilise a negative binomial model, with terms for treatment, continuous baseline rate, continuous baseline HbA_{1c}, continuous baseline eGFR and pre-existing insulin therapy as fixed effects and log(time at risk) as an offset. The results will be presented as a rate per patient-year. This analysis will be performed on the FAS (OC).

The baseline rate of symptomatic hypoglycaemic AEs with confirmed plasma glucose < 54 mg/dL and/or severe hypoglycaemic events confirmed by adjudication will be calculated based on the event rate during the 4 weeks prior to randomisation, see [section 6.7](#).

The analysis of the rate from Week 5 to Week 26 will include all on-treatment events from the start of Week 5 (Day 29) until the Week 26 cut-off date (as defined in [section 6.1](#)). This period will also define the time at risk.

The analysis of the rate from Week 1 to Week 26 will include all on-treatment events from the date of first study drug intake until the Week 26 cut-off date (as defined in section 6.1). This period will also define the time at risk.

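### For patients lost before Week 26 with no recorded stop date, the imputed stop date or Day 182 sets the hypoglycaemia time at risk, so unobserved days can enter the rate offset as event-free

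*SAP*

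**What the plan says.** Four SAP provisions act together.

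- **SAP 6.6.3** imputes a missing stop date. A documented end-of-treatment visit comes first, and a partial date with month and year has its own rule. Otherwise, as a general rule, for a patient "lost to follow-up it should be the date of the last visit + the longest treatment duration based on drug supply", plus one day.
- **SAP 6.1** defines the Week 26 cut-off date. For a patient who stopped early it is "The minimum between (drug stop date + X days) and day 182, if there is no week 26 visit date". For a patient regarded as still on treatment with no Week 26 visit, it is Day 182.
- **SAP Table 6.7: 1** sets X to 1 day for hypoglycaemia.
- **SAP 7.5.1.1** uses log(time at risk) as the offset. It counts events from Day 29 (or first intake) to the cut-off and adds: "This period will also define the time at risk".

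The protocol words the offset in 7.3.2.1 as "log (days of follow-up) as an offset"; its synopsis refers instead to days of exposure. Protocol 5.1.2 leaves the Week 26 cut-off "to be defined in the Trial Statistical Analysis Plan, TSAP". Protocol 7.5 says that no imputation is performed for this endpoint.

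**The concern.** Hypoglycaemia rates are built from AE data (protocol 5.3.5.1). A patient who has disappeared may report nothing further, yet under these rules the denominator runs on until the assumed drug supply is used up, or to Day 182. Each such day enters the model as a day at risk with no event.

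No visible rule stops the clock at the last date of ascertainment. The last contact date in SAP 6.1 cannot do so, because it is a maximum that itself includes last intake plus X days plus one.

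This sits poorly with an offset of follow-up days and with the observed-cases principle in SAP 6.6.1.2, under which "it is planned to analyse only the available data that were observed while patients were on-treatment".

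The two rates are confirmatory key secondary endpoints (H0,6 and H0,7) and carry 0.0225 of the 0.025 alpha within each dose. The rule understates the rate in any arm with such losses. The rate ratio is biased only to the extent that these losses differ between arms.

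**Working it through.** **Plan's own figure.** The documents give no planning figure for the hypoglycaemia rate. The only powered figure is for HbA1c (protocol 7.7): difference 0.3, SD 0.9, two-sided alpha 0.025. It reproduces: 225 per arm gives 90.05% power by t-test, and 225/0.94 = 239.4, rounded up to 240. It is used below only for arm size.

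**Inputs from the documents.** Flow Chart days: Visit 8 = 29, Visit 9 = 85, Visit 10 = 127, Visit 11 = 155, Visit 12 = 183. Medication is dispensed at Visits 8, 9, 10 and 12 but not at Visit 11, so supply lasts 56, 42 and 56 days from Visits 8, 9 and 10. Protocol 4.1.6 adds that a quantity "plus some reserve will be given to the patient", of unstated size r. Losses before Visit 8 are left out because the FAS needs an on-treatment HbA1c, first scheduled at Visit 8.

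**Days credited.** Imputed stop = last visit + supply + r + 1. Period end = min(stop + 1, 182). With r = 0, and with the last visit taken as last ascertainment:

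| Last visit | Imputed stop | Period end | Unobserved / credited, Week 5–26 | Unobserved / credited, Week 1–26 |
|---|---|---|---|---|
| Visit 8 | 29+56+1 = 86 | 87 | 58 / 59 | 58 / 87 |
| Visit 9 | 85+42+1 = 128 | 129 | 44 / 101 | 44 / 129 |
| Visit 10 | 127+56+1 = 184 | 182 | 55 / 154 | 55 / 182 |
| Visit 11 | 184 (Visit 10 supply) | 182 | 27 / 154 | 27 / 182 |

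An assumed reserve of 14 days raises the first two Week 5–26 entries to 72/73 and 58/115. The last two are already capped by Day 182. Counts are good to ±1 day, because the SAP numbers Week 26 as Day 182 and the Flow Chart as Day 183.

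**Simple person-time check.** Assume 2% of an arm is lost, spread equally over Visits 8–11, with r = 0. Mean observed days in Week 5–26 are (1+57+99+127)/4 = 71; mean credited days are (59+101+154+154)/4 = 117. The ratio is (0.98×154 + 0.02×71)/(0.98×154 + 0.02×117) = 152.34/153.26 = 0.994, an understatement of 0.6%.

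**Negative binomial estimate.** The model weights patients differently from raw person-time, so the arm-level score equation was solved: Σ w(y − μ)/(1 + αμ) = 0, with y = true rate × ascertained days and μ = fitted rate × credited days. Assumed ranges: 6–25 events per year, dispersion α 1–2, reserve 0–14 days, losses split equally over Visits 8–10 or Visits 8–11.

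| Arm lost this way (assumed) | Week 5–26 rate understated | Week 1–26 rate understated | Week 5–26, if half the unobserved days were in fact ascertained |
|---|---|---|---|
| 1% | 0.4–0.6% | 0.3–0.5% | 0.2–0.3% |
| 2% | 0.8–1.2% | 0.6–0.9% | 0.4–0.6% |
| 5% | 2.0–3.0% | 1.6–2.3% | 1.0–1.5% |

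**Effect on the comparison.** SE of the log rate ratio = √(2(1/μ + α)/225), with μ the expected count over 154 days (2.5 at 6 per year, 10.5 at 25 per year). This gives 0.10–0.15. With all loss in one arm, the Week 5–26 shift is 0.06–0.12 SE at 2% and 0.15–0.30 SE at 5%.

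**Simulation check.** With 240 per arm, 10 events per year, dispersion 1, a true ratio of 1 and 400 runs, the estimated ratio was about 1.00 with 2% or 5% loss in both arms, 0.99 with 5% against 2%, and 0.97 with 10% against 2%. Rejection at 0.0225 did not visibly change, but 400 runs (Monte Carlo SE about 0.007) cannot show a small change.

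**The case against.** The strongest objection is that this does not matter. A shift of 0.06–0.12 SE moves a nominal 0.0225 test under the null to only about 0.0227–0.0235, and that needs 2% loss in one arm and none in the other. Every loss rate here is assumed. This stands, and is why the point is minor.

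Several hypoglycaemia rules sit in SAP sections that are not public (5.4.6.3, 5.4.7). They may contain a limit on time at risk. This cannot be excluded; if one exists, a cross-reference in 7.5.1.1 would settle the matter.

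The inconsistency with the protocol is soft. The synopsis speaks of exposure, the cut-off is delegated to the SAP, and the observed-cases text concerns values rather than person-time. That is fair: it is a poor fit, not a plain contradiction.

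Days after the last visit may be partly observed through the e-diary, and an investigator may still report a severe event learned of later. This also stands. The figure of 58 of 59 days is illustrative, and the half-ascertained column shows the reduced effect.

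Finally, ending the period at last ascertainment removes late-reported on-treatment events from the confirmatory count, although protocol and SAP ask for all on-treatment events. That is a real cost. It keeps events and person-time on the same period, and the removed events can be shown in a sensitivity analysis.

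**Conclusion.** The concern holds for a narrow group: FAS patients lost to follow-up before Week 26 with no recorded stop date and no end-of-treatment visit. For them the public SAP text credits days that may be unobserved as event-free time at risk. The understatement of an arm's rate is of the order of 1% at 2% loss and at most about 3% at 5% loss, under the assumed event rates, dispersion, reserve and timing. The rate ratio moves only with between-arm differences in such losses. The conclusions on H0,6 and H0,7 are unlikely to depend on this. Because the number lost this way is not given and some SAP sections are not public, confidence is medium. The change is desirable rather than essential.

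**What to change.** In SAP 7.5.1.1, end both event counting and time at risk at the earliest of:

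1. drug stop date (observed or imputed) plus X days;
2. the Week 26 cut-off, including the Day 182 default;
3. the last date on which hypoglycaemia AEs were ascertained.

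Define the third as the last visit or contact with AE collection, or the last e-diary entry if diary events were still being reviewed into AEs. Contacts that collect only vital status do not count, since protocol 5.3.7 says AEs are no longer reported once that is all that is collected. Put on-treatment events reported as occurring after that date in a sensitivity analysis. Report the number of imputed stop dates by arm. Keep the imputed stop date for assigning other AEs to treatment.

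The cost is a few sentences; visit, contact and e-diary dates are already collected. The price is slightly less person-time and the removal of late-reported events from the confirmatory count.

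### The latest-possible end date for a partial antihypertensive stop delays the OC-H cut, so some blood pressures taken after discontinuation stay in the primary SBP/DBP analysis

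*SAP*

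**What the plan says.** SAP 6.6.3 covers partial dates for all concomitant therapies together and gives the aim: "the following derivations will be used to impute 'worst case' values". For stops: "If the day of the end date is missing then the end date is set to last day of the month", and "If the day and month of the end date are missing then end date is set to 31st December of the year". For starts: "If the day of the start date is missing the start date is set to first day of the month", and "If the day and month of the start date are missing then the start date is set to 1st January of the year".

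SAP 6.6.1.2 defines OC-H for blood pressure: "the OC-technique will be adapted to set values measured after a change in antihypertensive therapy to missing". The triggers are a dose change, "Initiation of additional antihypertensive medication" and "Discontinuation of antihypertensive medication".

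SAP Table 6.3: 1 makes OC-H on the FAS the primary analysis of SBP and DBP, with OC-AD as a sensitivity analysis. SAP 7.5.1.5 describes the confirmatory SBP/DBP analysis as FAS (OC), without the H. In Protocol 7.2 the two endpoints are H0,8 and H0,9, tested last.

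**The concern.** The imputation rule stretches the recorded course of a drug in both directions. That is cautious when the analysis removes data during intake, as OC-P does for paracetamol. OC-H works differently: it removes data after an event, so the date of the event sets the cut. When the event is a discontinuation, the latest possible date is the least cautious choice. Blood pressures measured between the true stop and the imputed stop are kept, although OC-H exists to remove them.

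What is at stake is whether the primary SBP/DBP analysis uses the data that its own rule describes. The OC-AD analysis cannot show the effect of the date rule, because it keeps every post-change value and adds off-treatment data.

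**Working it through.** The plan states no figure on this point, so there is nothing to reproduce. I applied the SAP 6.6.3 rules to a grid of dates.

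**Inputs**
- Blood pressure visits on planned days 7, 28, 84, 126 and 182 (SAP Table 6.7: 3).
- First dose on each of the 366 days of 2016, and a true change on each of days 1 to 181 after it: 366 × 181 = 66,246 scenarios. The even spread of dates is an assumption.

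**Stops**
- Delay = imputed stop − true stop.
- A visit is wrongly kept if true stop < visit date ≤ imputed stop.
- Month-only: the cut is never early. The delay is 0 to 30 days, mean 14.7. At least one post-stop visit is kept in 34.7% of scenarios and the Week 26 visit in 8.1%. Hand check: on average about 14.7 of the 181 possible stop days fall earlier in the Week 26 visit's own month, and 14.7 / 181 = 0.081.
- Year-only: the delay is up to 364 days on this grid, and a post-stop Week 26 value is kept in 75.1%.
- Example: first dose 10 March 2016, Week 26 on 8 September. A true stop on 2 September recorded as September 2016 is dated 30 September, so the 8 September value stays in.

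**Starts**
- Month-only: in 92.4% of scenarios the imputed start is on or after first dose and on or before the true start, so nothing contaminated is kept. In 27.0% of all scenarios at least one clean visit is removed instead.
- In the other 7.6%, all true starts in the first-dose month, the imputed start precedes first dose. Example: first dose 10 March, true start 20 March recorded as March 2016, imputed 1 March.
- Year-only: the imputed start precedes first dose in 74.9%.
- The visible SAP does not say what happens to a start dated before first dose. If it is taken as background therapy, later values stay in: on average 4.4 visits in the month-only case, always including Week 26. If any earlier change counts, the baseline and everything after it is removed.

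**Patients**
Neither the share of patients with an antihypertensive change nor the share of partial dates is in the documents. For illustration only, assume 10% of 720 change therapy by Week 26 and 2% to 10% of those lack the day:
- 720 × 0.10 × (0.02 to 0.10) = 1.4 to 7.2 patients with a partial date of any kind.
- If all were month-only stops, at least one wrongly kept visit: 1.44 × 0.347 to 7.2 × 0.347 = 0.5 to 2.5 patients.
- If all were month-only stops, a wrongly kept Week 26 value: 1.44 × 0.081 to 7.2 × 0.081 = 0.1 to 0.6 patients.
- If all were year-only stops, a wrongly kept Week 26 value: 1.44 × 0.751 to 7.2 × 0.751 = 1.1 to 5.4 patients. This is an extreme case.

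**The case against.** **Partial dates should be rare.** The Protocol Flow Chart has concomitant therapy reviewed at every visit, and Protocol 4.2 allows for dedicated eCRF pages for changes in antihypertensives. This stands, with the limit that Protocol 4.2 says only that such pages may be developed. It makes year-only dates for on-trial changes particularly unlikely.

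**The imputed date may not matter.** If SAP 7.5.1.5 is meant literally and the analysis is OC, values after a change stay in whatever date is imputed. The conflict with Table 6.3: 1 is real. SAP 6.6.1.2 presents OC-H as the form that OC takes for blood pressure, so OC-H looks intended, but the SAP should say so.

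**The endpoints are last in line.** SBP and DBP are tested confirmatorily only after a whole branch of the hierarchy succeeds. That is correct and limits the consequence.

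**SAP text is missing from view.** Sections 5.4 and 9.2 are not visible and could hold a further date rule or a reference date for a change.

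A reader might also infer that the rule is backwards for starts in general. It is not: in any month after that of first dose, an early start date makes OC-H cut early, which is the cautious side. Misdating to before first dose is confined to the first-dose month and to year-only starts, and its effect depends on a reading that the visible text does not settle.

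**Conclusion.** The point on stops holds. For a partial antihypertensive discontinuation, a stated rule never makes the OC-H cut early and usually makes it late, so post-discontinuation values can stay in the analysis. For starts, the finding is narrower: a start dated before first intake has no stated treatment in the visible SAP.

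The effect is very small. The scenario percentages rest on evenly spread dates, and the patient counts rest on assumed rates. A few patients at most, over three arms, is a reasonable expectation, and the true number is unknown.

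A reader might conclude that the retained values pull the treatment difference toward zero, or that the SBP and DBP tests are put at risk. The documents support neither: they give no rates or direction of antihypertensive changes by arm. This is a minor correction. It bears on the confirmatory result only if OC-H governs that analysis.

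**What to change.** Add to SAP 6.6.3, for OC-H only:
- Date a partial antihypertensive discontinuation at the earliest day in the recorded interval that is on or after first study drug intake and agrees with the visit-by-visit concomitant therapy record.
- Treat a partial start that could fall after first intake as occurring on or after first intake, unless the record shows that the drug was in use at Visit 6.

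Keep the present rule for concomitant therapy summaries and for OC-P, where it works in the cautious direction. Reconcile the data label in SAP 7.5.1.5 with Table 6.3: 1.

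The cost is a short SAP addition and a small programming change. The downside is that a few uncontaminated blood pressures are set to missing, and a patient whose partial date falls in the first-dose month may lose all post-baseline values from the OC-H analysis.
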